#### **Alternate strategies to address low bone density in AN**

**Recovery of weight and menses:** Although weight and menses recovery is associated with some increase in BMD, this increase is not sufficient to cause bone accrual to normalize, and BMD remains lower than in controls. Additionally, recovery can be hard to attain and sustain.

**Calcium and vitamin D supplementation:** Many studies have now shown that calcium and vitamin D supplementation is not sufficient to increase BMD in AN. BMD remains low in these women despite higher calcium and vitamin D intake than in controls

**PTH:** [REDACTED] increases BMD in post-menopausal women, however, PTH is not recommended in young people at this time given reports of osteosarcoma with PTH use in animal models.

**Alternate strategies to assess bone microarchitecture and strength:** MRI of the peripheral skeleton has lower resolution, longer scan time and increased susceptibility to image post-processing.

Describe how risks to subjects are minimized, for example, by using procedures which are consistent with sound research design and which do not unnecessarily expose subjects to risk or by using procedures already being performed on the subject for diagnostic or treatment purposes.

The intervention being provided involves no more than two shots a day given subcutaneously for a period of 6 months of a medication that has been shown to be safe in both adults with anorexia nervosa and in children with short stature and primary IGF-1 deficiency. Side effects, including

episodes of hypoglycemia, were uncommon in adult women with anorexia nervosa receiving rhIGF-1. Hypoglycemia is known to occur in anorexia nervosa per se, and was avoided in children receiving rhIGF-1 for short stature by administering the medication 30 minutes after meals. We plan to similarly administer rhIGF-1 30 minutes after breakfast and dinner. In a study [REDACTED] in 30 adult women with AN who received [REDACTED] rhIGF-1 [REDACTED], rhIGF-1 was well tolerated. Nadir blood glucose remained above 50 mg/dl after rhIGF-1 injection in all patients, and hypoglycemic symptoms were not reported acutely after rhIGF-1 injection or at any time throughout the study. Two subjects reported mild joint stiffness, which improved with dose reduction. In [REDACTED] study of adolescent girls with AN who received [REDACTED] rhIGF-1 [REDACTED], hypoglycemic symptoms were not reported. Other occasionally reported side effects of rhIGF-1 include bruising and redness at the injection site, lymphoid hypertrophy and snoring, lipohypertrophy, chronic middle ear effusions, raised intracranial pressure (headaches, vision changes, vomiting), slipped capital femoral epiphysis and progression of scoliosis in subjects who experience rapid growth, and arthralgias. Rotating injection sites will be advised and a close watch on other clinical features implemented. Also, as the drug is a pharmaceutical protein, anti-IGF-1 antibody formation can occur. 14 of 23 subjects treated for 2 years with the drug in one study experienced some degree of anti-IGF-1 antibody formation, though no clinical consequences (allergic reaction or loss of efficacy) were observed (from package insert). However, as with any exogenously administered protein, local or systemic allergic reactions may occur. Parents and subjects will be informed that such reactions are possible and that if an allergic reaction occurs, treatment should be interrupted and prompt medical attention sought. Because we will be giving a smaller dose of rhIGF-1 [REDACTED], we expect to see fewer side effects than indicated in the package insert. These risks of side effects are justified in light of the anticipated benefit of improved bone density and lowered immediate and lifetime fracture risk with treatment during this acute phase of disease.

A number of procedures will be instituted to protect against potential risk involved in this protocol. All patients will have pregnancy tests on admission prior to receiving any radiation or study medication. Subjects will also have serial pregnancy tests at every study visit. All study-related serious adverse events will be reported to the Subcommittee on Human Studies within 24 hours of occurrence.

Describe explicitly the methods for ensuring the safety of subjects. Provide objective criteria for removing a subject from the study, for example, objective criteria for worsening disease/lack of improvement and/or unacceptable adverse events. The inclusion of objective drop criteria is especially important in studies designed with placebo control groups.

Subjects will be instructed to call us if they develop any side-effects of the IGF-1 or risdrionate medication, or if symptoms of hypoglycemia are experienced. They will be advised to take 4 oz orange juice or two glucose pills if they are experiencing symptoms of hypoglycemia. Subsequent management will be decided based on the severity of the side-effect.

Serious side effects related to study drug will necessitate protocol discontinuation. If a subject develops a minor side effect, she will be asked to continue medications as per the protocol. Worsening of symptoms may necessitate temporarily withholding medication until other potential causes of symptoms are ruled out. Withholding medication for longer than one week will necessitate discontinuation of the study.

To minimize the risk from radiation, scans will not be performed on subjects until a negative pregnancy test result is obtained. If lab abnormalities are discovered, the subject and their physician, if authorized by the subject, will be notified.

If subjects are uncomfortable with any portion of any study visit, this portion will be discontinued or not performed.

Drop criteria for subjects:

1. Pregnancy (for any subject)
2. Medical instability, which will be determined by the study physician. Patients in this category will be assessed by the DSMB, and continue to be assessed according to study protocol
3. Serious study-related adverse event

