IGF-1 and Bone Loss in Women with Anorexia Nervosa

NCT # 01406444

Version Date: January 16, 2019

VI. Biostatistical Analysis

Experimental Endpoint

The primary endpoint will be PA spine BMD, and the primary analysis strategy will be to use a linear random effects model to estimate and test the effects of the three therapies on the study endpoints. The model that we propose is one where each patient has a linear trajectory from baseline to 6 months and then a possibly different linear trajectory from 6 months to a year. The 3 parameters that describe this trajectory are the intercept at baseline, the first slope, and the second slope. We assume that these three parameters have a multivariate normal distribution, with means dependent on the treatment group, the parameters of which we will estimate using SAS PROC MIXED. Since there are two slope parameters that depend on treatment, the mean slope in the first period and the mean slope in the second period, it is necessary to define the contrast of these parameters that will be used as the primary test of treatment effect. The contrast we will use will be the one that estimates the difference in the change in the endpoint at 12 months between the treatment groups. The advantage of using this analysis method rather than an analysis of covariance using only the 12 month and baseline data is that the method we propose will be more powerful and will also accommodate missing data better. It will give unbiased estimates whenever data are missing at random, while last observation carried forward (LOCF) or a complete case analysis would be biased (89). We will examine goodness of fit to this model using tests based on adding quadratic terms and by residual plots. If necessary we will add higher order terms to the model. We would use LOCF or complete case analysis as a secondary analysis. We use a model which has a break point at 6 months for all patients even for those on continuous therapy (placebo, risedronate) because having models that differ for the 3 treatments requires strong assumptions that lead to biases (90). An additional advantage of this model is that it is relatively easy to add baseline covariates. The primary analysis would be intent to treat. Patients who wish to stop therapy will be encouraged to return for all evaluations. Our primary comparison for BMD is PA spine BMD, and other comparisons are considered secondary. In this way, we avoid having to correct each comparison using a multiple comparison correction such as the Bonferroni inequality. We consider the comparison of sequential therapy to risedronate and the comparison of each of these to placebo to be separate scientific questions, so we do not plan to correct these 3 planned contrasts using a multiple comparison procedure (91).

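### If the protocol's stopping rules are applied as written, women stopped for a long drug hold or a serious drug-related event lose later DXA, and the intent-to-treat 12-month contrasts lean slightly toward an on-drug effect

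*Protocol*

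**What the plan says.** The protocol sets its stopping rules under Research Design and Methods, in reply to a form prompt that reads "Provide objective criteria for removing a subject from the study". Two rules matter here.

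- Serious effects: "Serious side effects related to study drug will necessitate protocol discontinuation".
- Long holds: "Withholding medication for longer than one week will necessitate discontinuation of the study".

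A list of drop criteria follows. Item 1 is pregnancy. Item 2 is medical instability, and it adds that these patients "continue to be assessed according to study protocol". Item 3 reads "Serious study-related adverse event" and carries no such clause. The long hold is not on the list.

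The SAP (section VI, Experimental Endpoint) says: "The primary analysis would be intent to treat. Patients who wish to stop therapy will be encouraged to return for all evaluations". The primary test is the between-group difference in 12-month change in PA spine BMD, from a linear random effects model with a break at 6 months. On missing data it says "It will give unbiased estimates whenever data are missing at random", and then "We would use LOCF or complete case analysis as a secondary analysis".

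**The concern.** The two documents do not meet. An intent-to-treat analysis needs outcomes from women who are off drug. The SAP asks for those outcomes only when the woman herself decides to stop. The protocol's wording for investigator-imposed stopping, read plainly, ends participation rather than treatment. The clause in item 2 shows that the authors could write continued assessment when they meant it, and they wrote it once.

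BMD is measured only at baseline, 6 and 12 months, so a removed woman loses one or both post-baseline scans. The model then predicts her remaining course from her own earlier values and from women in her arm who are mostly still on drug. If stopping costs some of the benefit, that prediction is too favourable. The contrast moves from the effect of being assigned a strategy toward the effect of staying on it.

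The secondary analyses do not repair this. LOCF tests a different assumption, but the SAP itself calls LOCF and complete case biased, leaves open which will be run, and neither changes the primary contrast.

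**Working it through.** **Inputs from the SAP, Power Analyses.** Evaluable women: 36, 36 and 18 (from 40, 40 and 20 with 10% drop-out). SD 2.69%. Twelve-month change: sequential 4.8%, risedronate 2.3%. At 6 months, rhIGF-1 with oral contraceptives gained 2.54%, which was 3.05% over placebo. Risedronate fell 0.3% between months 6 and 12.

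**The plan's own figure.** For sequential versus risedronate, the standard error is 2.69 × √(2/36) = 0.63. A two-sided 5% t-test at a difference of 2.5 has 97% power, so the stated power above 80% is met. Against placebo the standard error is 2.69 × √(1/36 + 1/18) = 0.78.

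**Effects versus placebo, two routes.**
- Placebo at 2.54 − 3.05 = −0.51 (a 6-month figure, assumed to hold at 12 months) gives sequential 4.8 + 0.51 = 5.31 and risedronate 2.3 + 0.51 = 2.81.
- The SAP's statement that the sequential–placebo difference is about twice 2.5 gives 5.0 and 2.5.

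**Assumptions not in the documents.** Let dS and dR be the shares removed from the sequential and risedronate arms, and k the share of benefit kept at 12 months. Removed placebo women lose nothing. Removed women are credited with their arm's on-drug mean.

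**Scenario A: all benefit lost, whenever removed (k = 0).**
- Sequential − risedronate: (1 − k)(5.31 dS − 2.81 dR)
- Sequential − placebo: (1 − k)(5.31 dS)
- Risedronate − placebo: (1 − k)(2.81 dR)

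**Scenario B: removed just after month 6, 6-month value held.** Each woman's own 6-month scan is in the model, so only the second period is mispredicted.
- Sequential: 0.05 × (4.8 − 2.54) = 0.113
- Risedronate: 0.05 × (−0.3) = −0.015
- Sequential − risedronate: 0.113 + 0.015 = 0.128

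The 4.8 and the 2.54 come from different studies, so B is illustrative.

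| Shift in points, 5% removed per active arm | A (5.31 / 2.81) | A (5.0 / 2.5) | B | SE |
|---|---|---|---|---|
| Sequential − risedronate | 0.125 | 0.125 | 0.128 | 0.63 |
| Sequential − placebo | 0.27 | 0.25 | 0.11 | 0.78 |
| Risedronate − placebo | 0.14 | 0.125 | −0.015 | 0.78 |

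Scenario A is linear in the removal rate. At 10%, which would make the entire planned drop-out investigator-imposed, the three shifts are 0.25, 0.50–0.53 and 0.25–0.28. At 2.5% (1 of 40) with 5.31 and 2.81 they are 0.06, 0.13 and 0.07. All halve at k = 0.5 and vanish at k = 1.

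**Direction for sequential − risedronate.** Under A with unequal removal (sequential v risedronate, of 40 each): 2 v 1 gives 0.266 − 0.070 = +0.20; 1 v 2 gives 0.133 − 0.141 = −0.01; 1 v 3 gives 0.133 − 0.211 = −0.08. The sign turns at dR/dS = 5.31/2.81 = 1.89, or 5.0/2.5 = 2.0. Differential retention matters too: at 1 of 40 each, the range is +0.13 (only sequential stoppers lose benefit) to −0.07 (only risedronate stoppers do).

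**Power.** With 10% removed from both active arms and all benefit lost, sequential versus risedronate falls to 2.5 − 0.25 = 2.25, where power with 36 per arm is 94%. For risedronate versus placebo, 2.81 − 0.28 = 2.53 gives 89%.

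**The case against.** The strongest reply is that the rules may concern drug only. They sit among instructions on managing medication, the wording is loose, the long hold is not a listed drop criterion, and item 2 shows that a dropped woman can still be assessed. The prompt about removal belongs to the form and is not the plan's own rule. The SAP states intent to treat without exception. This stands in part: what is shown is an ambiguity, and loss of data is not proven. But no sentence in either document provides for scanning women stopped for a long hold or a serious drug-related event.

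A reader might infer that every woman taken off drug by the investigators leaves follow-up. The documents do not support that. Medically unstable women are expressly kept under assessment, and pregnant women could not be scanned under any rule.

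A reader might also take the full-loss figures against placebo as expected values. They are upper-end scenarios. The model uses each woman's own scans, so removal after month 6 leaves only the second slope to be predicted. The protocol also notes that bisphosphonates stay in bone for years, so some benefit may persist.

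Finally, removal may be rare. The protocol reports good tolerability in 30 women with AN on rhIGF-1 and 16 on risedronate. If none of them would have met these rules (an assumption; no count is given), the one-sided 95% upper limits are 1 − 0.05^(1/30) = 9.5% and 1 − 0.05^(1/16) = 17%. Low rates are plausible, but these samples cannot establish them.

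**Conclusion.** The point holds as a cheap improvement, conditional on the stopping rules being applied as written. It covers women stopped for a hold of more than one week or a serious drug-related event. For them, lost DXA would make the 12-month contrasts lean toward an on-drug effect.

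The size is undocumented, because the plan gives only an overall 10% drop-out, with no split by cause or arm. With an assumed 5% removed per active arm, the active comparison shifts by about 0.13 points, roughly a fifth of its standard error. The largest shift against placebo is 0.27, about a third of its standard error.

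Two further inferences should be resisted. One is that the plan systematically favours sequential therapy over risedronate: with all benefit lost, the sign reverses once risedronate removals reach about twice sequential removals. The other is that the trial would be underpowered: power stays high even when the whole planned drop-out is attributed to these rules.

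**What to change.** Keep every safety rule for holding or stopping drug. Amend the protocol so that a hold of more than one week, or a serious drug-related event, stops study drug only. State that women who still consent have the scheduled 6- and 12-month DXA after a negative pregnancy test, and that these values enter the primary analysis. In the SAP, extend the follow-up sentence to women whose drug is stopped by the investigators. As an option, add a placebo-reference or delta-adjusted sensitivity analysis for values still missing.

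The cost is one or two sentences in each document and some retention effort, since the DXA visits are already scheduled. The estimated effect may be slightly smaller, which is what an intent-to-treat estimate should show if stopping loses benefit. If the sponsor already means drug only, the amendment simply says so.

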### **FORESEEABLE RISKS AND DISCOMFORTS**

Provide a brief description of any foreseeable risks and discomforts to subjects. Include those related to drugs/devices/procedures being studied and/or administered/performed solely for research purposes. In addition, include psychosocial risks, and risks related to privacy and confidentiality. When applicable, describe risks to a developing fetus or nursing infant.

**Complications of surgical and non-surgical procedures:** There is a risk of superficial bruising and discomfort at the venepuncture site. Rarely, fainting (from a vasovagal episode) or a treatable infection may occur.

Subjects will have DXAs to measure BMDs of the whole body, lumbar, spine, hip and radius during the study. This involves minimal radiation (~0.02 mSv for entire study), less than 1% of the background radiation received/person/year in the US. MDCT of the spine entails radiation of <1.8 0.9 mSv. The radiation dose of HR-pQCT of the radius and tibia is 0.06-0.08 mSv per measurement which is less than 2% of the annual background radiation from the earth and sky. The cross-sectional CT of the abdomen and mid thigh entails two CT slices and 0.18 mSv. The effective dose for three such scans in one year (baseline, 6 and 12 months) is about 18% of the dose an average person receives from background radiation in a year. The total effective dose from all radiologic exams for the entire study (4 DXAs, 3 HR-pQCTs, 2 MDCTs, and 3 thigh and abdomen cross-sectional CTs) will be slightly about 143% of the effective dose (3mSv) an average person is exposed to from background radiation per year.

There is no direct evidence that this amount of radiation exposure will cause harmful effects. To protect from scatter radiation during the MDCT, the patients will be asked to wear a lead vest and a lead skirt to minimize radiation to other parts of their body during scanning. Exposure of sensitive pelvic organs is not expected as only the L1 vertebral body is exposed. Pregnancy needs to be ruled out before these tests are done to avoid the risk of radiation exposure to the unborn baby. A urine pregnancy test will be performed prior to the x-ray for all subjects.

**Complications of medications:** rhIGF-1 will be administered [REDACTED]. RhIGF-1 is approved by the FDA for use in children with primary IGF-1 deficiency [REDACTED]. As per the package insert for rhIGF-1 for this indication: mild or moderate hypoglycemia (very rarely

severe), thought to be related to the drug's insulin-like activities, may occur in up to 42% of patients on this medication during the course of therapy. More severe hypoglycemia is rare. Risk of hypoglycemia is generally avoided when a meal or snack is consumed 30 minutes prior to rhIGF-1 administration. All subjects will be familiarized with signs and symptoms of hypoglycemia and timely management of the same. Measures to treat hypoglycemia will be described (carry a source of carbohydrates at all times, e.g. a juice box or glucose tablets). Subjects with a serum IGF-1 level that is not within the normal range for age will receive a 25% dose adjustment. For those patients requiring a 25% dose increase to maintain IGF-1 levels within the normal range, we will contact subjects by phone to assess for side effects from the higher dose. We will monitor IGF-1 levels at all visits for all subjects taking rhIGF-1.

The potential risk of risedronate in this study is not greater than that associated with its common use in clinical practice. These risks include abdominal or stomach pain, skin rash, diarrhea, headache and joint pain. Less common side effects include severe abdominal pain or stomach pain, stomach cramping, belching, bone pain, blurred vision or change in vision, chest pain, constipation, cough, dizziness, dry eyes, fever, general feeling of discomfort or fullness, leg cramps, nausea, ringing in the ears, swelling of feet or lower legs, and weakness. On rare occasion, red sore eyes have been reported. Risedronate was well tolerated in the 16 women with AN who participated in [REDACTED] studies; there were no cases of esophagitis, despite a high prevalence of concomitant bulimia. Although the long-term risk of risedronate in young women is unknown, bisphosphonates have been used in premenopausal women to treat osteopenia due to glucocorticoids. In addition, these medications are used widely in the community and it is essential that their efficacy be assessed. Bisphosphonates remain in the bones for many years after administration, and it is unknown whether bisphosphonates may be secreted from bone during pregnancy or breastfeeding.

There may be other risks of rhIGF-1 and risedronate that are currently unknown.

**Oral calcium** can cause constipation and a metallic taste in the mouth.

**Vitamin D** in the doses being administered does not cause any side effects.

**Estrogen** can cause headache, breast tenderness, abnormal withdrawal bleeding, bloating and cramping, nausea and mood swings. The estrogen patch may also cause skin irritation. In a very small percentage of patients, blood clot or stroke have been reported.

## **EXPECTED BENEFITS**

Describe both the expected benefits to individual subjects participating in the research and the importance of the knowledge that may reasonably be expected to result from the study. Provide a brief, realistic summary of potential benefits to subjects, for example, "It is hoped that the treatment will result in a partial reduction in tumor size in at least 25% of the enrolled subjects." Indicate how the results of the study will benefit future patients with the disease/condition being studied and/or society, e.g., through increased knowledge of human physiology or behavior, improved safety, or technological advances.

[REDACTED]

IGF-1 and Bone Loss in Women with Anorexia Nervosa

NCT # 01406444

Version Date: January 16, 2019

VI. Biostatistical Analysis

Experimental Endpoint

The primary endpoint will be PA spine BMD, and the primary analysis strategy will be to use a linear random effects model to estimate and test the effects of the three therapies on the study endpoints. The model that we propose is one where each patient has a linear trajectory from baseline to 6 months and then a possibly different linear trajectory from 6 months to a year. The 3 parameters that describe this trajectory are the intercept at baseline, the first slope, and the second slope. We assume that these three parameters have a multivariate normal distribution, with means dependent on the treatment group, the parameters of which we will estimate using SAS PROC MIXED. Since there are two slope parameters that depend on treatment, the mean slope in the first period and the mean slope in the second period, it is necessary to define the contrast of these parameters that will be used as the primary test of treatment effect. The contrast we will use will be the one that estimates the difference in the change in the endpoint at 12 months between the treatment groups. The advantage of using this analysis method rather than an analysis of covariance using only the 12 month and baseline data is that the method we propose will be more powerful and will also accommodate missing data better. It will give unbiased estimates whenever data are missing at random, while last observation carried forward (LOCF) or a complete case analysis would be biased (89). We will examine goodness of fit to this model using tests based on adding quadratic terms and by residual plots. If necessary we will add higher order terms to the model. We would use LOCF or complete case analysis as a secondary analysis. We use a model which has a break point at 6 months for all patients even for those on continuous therapy (placebo, risedronate) because having models that differ for the 3 treatments requires strong assumptions that lead to biases (90). An additional advantage of this model is that it is relatively easy to add baseline covariates. The primary analysis would be intent to treat. Patients who wish to stop therapy will be encouraged to return for all evaluations. Our primary comparison for BMD is PA spine BMD, and other comparisons are considered secondary. In this way, we avoid having to correct each comparison using a multiple comparison correction such as the Bonferroni inequality. We consider the comparison of sequential therapy to risedronate and the comparison of each of these to placebo to be separate scientific questions, so we do not plan to correct these 3 planned contrasts using a multiple comparison procedure (91).

Markers of bone metabolism

The analysis will focus on 2 periods – one from 0 to 6 months, where we will have 2 post-treatment measurements, and one from 6 to 12 months, where we will also have 2 post-treatment measurements. The primary analysis will be to compare the bone markers in patients post risedronate values to the post-rhIGF-1 values using a repeated measures analysis of covariance where the covariant is the baseline value for each period and the primary question is on average over the period whether there is a difference in markers. The significance of the analysis in the first period is whether these markers are affected differently by the 2 treatments, rhIGF-1 and risedronate. The second question, for the second period, is whether pre-treatment with rhIGF-1 changes the response to risedronate.

Muscle mass

Body composition parameters (thigh muscle mass, total, subcutaneous and visceral abdominal fat) by cross-sectional CT at 0, 6, and 12 months. The primary analysis of this measure will be by analysis of covariance with the 6-month measures as the dependent variable and the baseline measure as a covariate.

Bone microarchitecture and strength

There will be two analyses of these data, one comparing 6 months to baseline with an analysis of covariance, and one comparing 12 months to baseline. The first analysis isolates the effect of IGF-1 vs. risedronate and placebo. The second measures the effect of the sequential therapy.

Power Analyses: Determination of an n of 100 subjects for the primary aim.

The primary aim of the study is Specific Aim 1A, and the primary endpoint will be PA spine BMD. This aim will compare rhIGF-1 followed by risedronate (for anabolic consolidation and further BMD increases) to risedronate alone and to placebo. The study will determine 1) whether sequential therapy is superior to risedronate, 2) whether sequential therapy is superior to placebo and 3) whether risedronate administration is superior to placebo. A total of 100 patients will enter this three treatment parallel-design study. With 36 evaluable patients in each of the two active treatment groups (assuming a 10% drop-out rate), the probability is >80% that the study will detect a difference between sequential therapy and risedronate at a two-sided 5% percent significance level, if the true difference between the treatments is 2.5%. This is based on the assumption that the SD of the response variable (BMD in women with AN receiving oral contraceptives) is 2.69%, as we found in our previous study (24) and on the 2.5% difference we found in our interim analysis of our preliminary study of sequential rhIGF-1 followed by risedronate (4.8%) compared with risedronate alone (2.3%) at 12 months. In addition, it is consistent with the increase of 2.54% from baseline (3.05% compared with placebo) at the PA spine at 6 months in subjects who received rhIGF-1 and OCPs (see Background and Figure 1). Risedronate increased BMD at 6 months followed by a decrease of 0.3% between 6 and 12 months (see Progress Report). Thus, we expect that the principal difference between sequential therapy and risedronate alone will be the 6-month effect we found of rhIGF-1 in this estrogen-treated population of 2.54% plus 0.4%. With 36 subjects in each treatment group and 18 subjects in the placebo group (assuming a 10% drop-out rate), we expect the difference between the rhIGF-1 followed by risedronate and placebo groups to be approximately twice that between the two treatment groups and therefore we will have adequate power even though we have half the number of subjects in the placebo group. The power for this comparison will be 89%. We also have >80% power to detect a difference between the risedronate and placebo groups. These sample size estimates were based on using an analysis of covariance as the analysis method. The power calculated with this method will be somewhat less than the power achieved using the random effects model we propose.

Markers of bone metabolism

With 76 evaluable patients randomized between risedronate and rhIGF-I for the first six months, we will have an 80% chance of detecting a difference of 13 units in PINP. This represents a difference of 25% of the baseline value of PINP in patients with AN. For the difference between these groups (sequential therapy and risedronate) over the 12-month period, we will be able to detect a difference of 0.13 units in CTX at a 5% significance level. For CTX, the difference is 19% of the baseline level. The power calculation was based on a repeated measures analysis of covariance with the baseline value as a covariate and two post baseline measurements. We used the programs provided by [REDACTED] (92). The variance covariance matrix of the measurements were (350,360;360,535) for PINP and (0.05,0.012;0.012,0.049) for CTX and are from our pilot study with 36 patient completers in the risedronate only and double placebo groups.

Muscle mass

With 40 women in the rhIGF-1 group and 20 in the placebo group, the probability is 80% that the study will detect a treatment difference at a two-sided 5.0% significance level, if the true difference between the treatments is 4.3%. This is based on the assumption that the SD of the response variable is 5.2%, as we found when we examined the 6-month change from baseline in women of reproductive age receiving placebo (93). We conclude that this is feasible because it is smaller than the 6% change in fat-free mass that was produced by IGF-1 in our previously published study in patient with AN (24).

GH and IGF-1

With 40 women in the rhIGF-1 group and 20 in the placebo group, the probability is 80 percent that the study will detect a treatment difference at a two-sided 5.0% significance level, if the true difference between the treatments is 0.7 times the SD of change from baseline.

Bone microarchitecture: Spine

The literature on trabecular thickness uses percent change as the unit of effect. With 36 evaluable patients in each treatment group the 95% confidence interval on the change in trabecular thickness of the spine will be 2.7% for each of the two active treatments based on Graeff *et al.* who estimated the difference between two spine microarchitectural endpoint measurements 12 months apart to be 8.8%, depending on the measure, and the SD of the change of 8.2% (73). Based on this we will be able to estimate trabecular thickness at the spine to sufficient precision to be confident as to whether the treatments affect this variable.

Radius and Tibia

With 40 patients in each treatment group and 20 in the placebo group entering the study and a 10% drop-out rate, the probability is 80 percent that the study will detect a treatment difference at a two-sided 5.0% significance level, if the true difference between the treatments is 2%. This assumes that the within subject SD is 3%, which is the interscan variation described for the instrument (94). If the within patient SD is twice this, e.g. 6%, we would be able to detect a change in trabecular thickness of 4%, which is smaller than the difference between women with and without fractures of 6% (95). In addition, for both of the comparisons with placebo, we will be able to detect a 2.5% difference between groups with an 80% probability. If the within patient SD is twice this, we would be able to detect a change in trabecular thickness of 5%. Thus, we think that this measurement has the potential of detecting small clinically important differences in this parameter. The SD of 6% is greater than the SD found in the EUROFORS study using similar high-resolution CT scanners after 6 months of treatment with PTH of 5.6% (73). In the powering, we focus on the pairwise comparisons of the treatment arms because the scientific questions are distinct for each pairwise comparison.

Bone strength (FEA)

The literature on FEA standardizes measurements using the population SD standard deviation. We refer to one population SD as a unit. For strength, with 36 evaluable patients in each treatment group the 95% confidence interval of the change in FEA of the spine will be ± 0.33 units for each of the two active treatments. This is based on Graeff *et al.* who estimated the difference between two measurements 12 months apart to be 0.43 to 0.82 units, depending on the measure, and the SD of the change of one unit (73). Orwoll *et al.* demonstrated that 1 unit produces a hazard ratio of 3.196. Based on this, we will be able to estimate FEA to sufficient precision to be confident as to whether the treatments affect this variable.

Exploratory Aim

Sequential therapy with physiologic rhIGF-1 administration replacement followed by a bisphosphonate will increase spine bone strength in women with AN compared with bisphosphonate or placebo. We will develop a novel FEA model to determine spine strength using high resolution MDCT data. [REDACTED] has recently published the development and validation of such a model for wrist and leg strength in AN (78), and [REDACTED] is a world-renowned expert in this area (82,84,96) and will serve as a consultant on this project. For power and data analyses, please see sections on FEA of wrist above.
